#### 5.5. Justification for Dose

Human PK parameters, including clearance (CL, Q) and volume of distribution (V1, V2) were predicted using the allometric scaling from monkey PK parameters, with a fixed exponent of 0.8 and 1 for clearance and volume, respectively (Wang and Prueksaritanont 2010).

The minimal pharmacology active dose (PAD) is determined from the rat DRG pTrkA signaling data, and the biologically effective dose (BED) is defined from an integrated review of the preclinical data package detailed in the IB that included the following measures:

- A prior clinical study with a nonselective small molecule TrkA inhibitor indicated that very high coverage over the TrkA IC50 may be required for efficacy (Loudon et al. 2018). The plasma concentration of LY3478006 required to achieve 30-fold coverage

over the human pTrkA IC50 in skin is approximately 37.4 µg/mL (human pTrkA in vitro IC50 = 0.83 nM, and assumes a typical antibody 10% skin:plasma partition coefficient).

- The plasma concentration at the minimal effect dose (MED) of 10 mg/kg in the rat intra-articular CFA-induced gait deficit model is 46.2 µg/mL after 3 days postdose.
- The plasma concentration required to achieve significant inhibition of DRG pTrkA signaling at 3 days postdose is 5.7 µg/mL.

The predicted BED of 65 mg QW, 150 mg Q2W, and 400 mg Q4W are predicted to achieve a Ctrough above the minimal 30-µg/mL threshold for the entire dosing interval once steady state is reached. The predicted PAD of 10 mg QW, 30 mg Q2W, and 80 mg Q4W are predicted to achieve Ctrough above the minimal 5.7-µg/mL threshold for the entire dosing interval once steady state is reached. These predictions apply to both IV and SC administration as they are based upon Ctrough from a 2-compartment linear PK model with a bioavailability of 83%. Once clinical PK data (including SC bioavailability) become available, the predicted BED will be refined for both the IV and SC dosing regimens. It is currently proposed that future multiple dose studies will start with a monthly (Q4W) dosing regimen

A single-dose monkey PK/PD study was performed at 0.1, 0.5, and 3 mg/kg IV to explore the relationship between dose, exposure, and PD using the same assay and methodology compared to the single ascending dose study: every animal was its own control and 4 postdose skin punch biopsies were collected. These data were useful to establish the time points for the collection of the postdose skin punch biopsies in healthy subjects, but were not informative enough to build a PK/PD model as the 3 doses explored provided similar PD effect.

To establish safety and tolerability of LY3478006 and evaluate the dose/exposure-response relationship (via skin punch biopsies to measure pTrkA and tTrkA), a wide dose range for LY3478006 (10, 30, 100, 300, 600, and 1000 mg, IV) is proposed for the single ascending dose study performed in healthy subjects. In addition, a single 100-mg SC dose is planned to be administered to define the bioavailability of LY3478006. However, based on emerging data a higher dose may be administered but will not exceed 300 mg.

The no-observed-adverse-effect level (NOAEL) for LY3478006 in the monkey 3-month toxicology study is 170 mg/kg IV. In rats, adverse skin lesions consistent with self-trauma (persistent scratching) limited the dosing of LY3478006 to approximately 1 month, and erosion/ulceration of the tongue was present at all doses tested in small numbers of rats (changes which were also consistent with injury/trauma as opposed to direct toxicity of the test article on the tongue). Therefore, no NOAEL was identified in rat although the adverse changes are of questionable human relevance and are clinically monitorable. As shown in [Table OHAA.2](#), the proposed starting dose of 10 mg IV and maximum dose of 1000 mg IV have a sufficiently large margin of safety in the monkey both in terms of dose and exposure. The starting dose of 10 mg is anticipated to be 8-fold lower than the PAD and the top dose of 1000 mg is anticipated to be 2.5-fold higher than the BED. Taking the assumption that the predicted PAD dose of 80 mg Q4W provides 50% of the effect (assuming ED50 value based on 50% TE in DRG): with a hill factor of 1, the 400-mg Q4W projected BED dose is predicted to provide around ED85 and the

top dose of 1000 mg is predicted to be around ED90. The planned maximum dose (1000 mg IV) in humans was selected as 1/10th the repeat dose monkey NOAEL (and highest dose tested in rat) based on dose (mg/kg). Pharmacokinetic projections predict that drug exposures at the maximum dose of 1000 mg IV will remain below 1/7th the exposures at the NOAEL in the monkey GLP toxicology study (dosed for 3 months). Potential treatment-emergent changes in cutaneous sensation are expected to be readily evident to subjects and, in addition, scheduled neurologic exams will include assessments for changes in cutaneous sensation. Scheduled physical examinations will also include inspection of the oral cavity.

**Table OHAA.2. Margin of Safety for Intravenous Administration of LY3478006 Based on Administered Dose and Predicted Human Exposure and Actual Animal Exposure**

	Dose (mg/kg)	Dose Multiple a	AUC (µg·hr/mL)	AUC Exposure Multiple b	C max (µg/mL)	C max Exposure Multiple c
Human Starting dose (10 mg IV)	0.167	–	1006	–	2.9	–
Rat LOAEL skin/tongue d	60 (SC)	359	63600	63.2	824	284
Rat Highest Dose Tested	170 (IV)	1018	269000	267	4470	1541
Monkey NOAEL e	170 (IV)	1018	728000	724	7230	2493
Human Maximum dose (1000 mg IV)	16.7	–	100581	–	289.9	–
Rat LOAEL skin/tongue d	60 (SC)	3.6	63600	0.63	824	2.8
Rat Highest Dose Tested	170 (IV)	10.2	269000	2.7	4470	15.4
Monkey NOAEL e	170 (IV)	10.2	728000	7.2	7230	24.9

Abbreviations: AUC = area under the serum concentration × time curve; Cmax = maximal serum concentration; IV = intravenous; LOAEL = lowest-observed-adverse-effect level; NOAEL = no-observed-adverse-effect level; SC = subcutaneous.

a Dose multiple is the dose in animals/dose in humans based on mg/kg and human body weight = 60 kg. Exposure multiple is the calculated AUCtau,ss in animals / predicted AUC0-∞ in humans (see Table 4.10 in the IB for predicted human PK).

b AUC multiple = mean AUCtau observed after the last dose in animal/predicted mean AUC0-∞ after a single dose in human. AUC in rats presented is calculated as 0-96hr. AUC in monkeys presented is calculated as 0-168hr.

c Cmax multiple = mean Cmax observed after the last dose in animal/predicted mean Cmax after a single dose in human.

d Determined in a 1-month repeat dose toxicity study.

e NOAEL determined in a 3-month repeat dose toxicity study.

The margin of safety table presented above is based on predicted exposure following IV administration (100% bioavailability) and therefore provides an appropriate margin for SC dosing, where bioavailability cannot be higher than 100%.

## 6. Study Population

Eligibility of subjects for the study will be based on the results of screening medical history, physical examination, vital signs, clinical laboratory tests, and ECG.

The nature of any conditions present at the time of the physical examination and any preexisting conditions will be documented.

Screening may occur up to 28 days prior to enrollment. Subjects who are not enrolled within 28 days of screening may be subjected to an additional medical assessment and/or clinical measurements to confirm their eligibility. Prospective approval of protocol deviations to recruitment and enrollment criteria, also known as protocol waivers or exemptions, are not permitted.

### 6.1. Inclusion Criteria

Subjects are eligible for inclusion in the study only if they meet all of the following criteria at screening and/or enrollment:

- [1] are overtly healthy males or female Japanese or non-Japanese subjects, as determined by medical history and physical examination.
  - [1a] Male subjects must agree to adhere to contraception restrictions specified in Section 6.3.4.
  - [1b] Female subjects:  
Women not of childbearing potential may participate and include those who are infertile due to surgical sterilization (hysterectomy without bilateral oophorectomy or confirmed tubal occlusion [not tubal ligation]).
- [2] Are aged 18 to 55 years (20 to 55 years for Japanese subjects), inclusive, at screening.
- [3] Have a body mass index (BMI) of 18.0 to 32.0 kg/m^2, inclusive, at screening.
- [4] Have clinical laboratory test results within normal reference range for the investigative site, or results with acceptable deviations that are judged to be not clinically significant by the investigator.
- [5] Have venous access sufficient to allow for IV drug delivery and blood sampling as per the protocol.
- [6] Are reliable and willing to make themselves available for the duration of the study and are willing to follow study procedures and CRU procedures.
- [7] Have given signed informed consent.

Additional criteria to qualify as Japanese subjects in this study:

- [8] To qualify as a subject of Japanese origin (first-generation Japanese), the subject, the subject's biological parents, and all of the subject's biological grandparents must be of exclusive Japanese descent and have been born in Japan.

## 6.2. Exclusion Criteria

Subjects will be excluded from study enrollment if they meet any of the following criteria at screening:

- [9] Are investigative site personnel directly affiliated with this study and their immediate families. Immediate family is defined as a spouse, biological or legal guardian, child, or sibling.
- [10] Are Eli Lilly and Company (Lilly) employees or employees of third-party organizations involved with the study who require exclusion of their employees.
- [11] Are currently enrolled in a clinical study involving an investigational product or any other type of medical research judged not to be scientifically or medically compatible with this study.
- [12] Have participated, within the last 30 days, in a clinical study involving an investigational product. If the previous investigational product has a long half-life, 5 half-lives or 30 days, whichever is longer, should have passed.
- [13] Have previously completed or withdrawn from this study or any other study investigating LY3478006, and have previously received the investigational product.
- [14] Have known allergies to LY3478006, related compounds or any components of the formulation, or history of significant atopy.
- [15] Have clinically significant abnormal ECG results constituting a risk when taking the investigational product, as determined by the investigator.
- [16] Have persistent abnormal blood pressure and/or pulse rate as determined by the investigator.
- [17] Have evidence of orthostatic hypotension defined as decrease in systolic or diastolic of  $\geq 20$  mmHg or  $\geq 10$  mmHg, respectively.
- [18] Have a history or presence of cardiovascular, respiratory, hepatic, ophthalmological, renal, gastrointestinal, endocrine, hematological, neurological, or psychiatric disorders capable of significantly altering the absorption, metabolism, or elimination of drugs; of constituting a risk when taking the investigational product; or of interfering with the interpretation of data.
- [19] Have a history or presence of mononeuropathy, polyneuropathy, or autonomic neuropathy.

- [20] Subjects who are not suitable for measurement of pupil size by the study specified methodology.
- [21] Regularly use known drugs of abuse (including cannabis) and/or show positive findings on urinary drug screening.
- [22] Show evidence of human immunodeficiency virus (HIV) infection and/or positive human HIV antibodies.
- [23] Have liver function test (aspartate aminotransferase [AST], alanine aminotransferase [ALT], alkaline phosphatase [ALP], total bilirubin [TBL]) above the upper limit of normal (ULN) at screening.
- [24] Show evidence of hepatitis C and/or positive hepatitis C antibody.
- [25] Show evidence of hepatitis B and/or positive hepatitis B surface antigen.
- [26] Are women who are lactating.
- [27] Have used or intend to use over-the-counter or prescription medication (including herbal medications) within 7 days prior to dosing or during the study with the exception of: vitamins and mineral supplements (not providing >100% of the recommended daily allowance), hormone replacement, and/or occasional paracetamol/acetaminophen. If this situation arises, inclusion of an otherwise suitable subject may be at the discretion of the sponsor.
- [28] Have donated blood of more than 500 mL within the last month.
- [29] Have an average weekly alcohol intake that exceeds 21 units per week (males) and 14 units per week (females), or are unwilling to stop alcohol consumption from 48 hours prior to dosing (1 unit = 12 oz or 360 mL of beer; 5 oz or 150 mL of wine; 1.5 oz or 45 mL of distilled spirits).
- [30] Consume more than 10 cigarettes per day or the equivalent, and/or are unable or unwilling to refrain from smoking, vaping, or nicotine use (including replacement therapy) during CRU admissions.
- [31] Have received treatment with biologic agents (such as monoclonal antibodies, including marketed drugs) within 3 months or 5 half-lives (whichever is longer) prior to dosing.
- [32] Have significant allergies to humanized monoclonal antibodies.
- [33] Have clinically significant multiple or severe drug allergies, or intolerance to topical corticosteroids, or severe post treatment hypersensitivity reactions (including, but not limited to, erythema multiforme major, linear IgA dermatosis, toxic epidermal necrolysis, or exfoliative dermatitis).
- [34] Have had lymphoma, leukemia, or any malignancy within the past 5 years except for basal cell or squamous epithelial carcinomas of the skin that have been resected with no evidence of metastatic disease for 3 years.
- [35] Have had breast cancer within the past 10 years.

[36] In the opinion of the investigator or sponsor, are unsuitable for inclusion in the study.

### **6.3. Lifestyle and/or Dietary Requirements**

Throughout the study, subjects may undergo medical assessments and review of compliance with requirements before continuing in the study.

#### **6.3.1. Meals and Dietary Restrictions**

Subjects should fast for at least 4 hours prior to study drug administration and are required to remain recumbent for approximately 2 hours (unless otherwise required for procedures) after study drug administration and remain sedentary in a bed or chair for the subsequent 4 hours for observation. Subjects are permitted to have a meal approximately 1 hour following the completion of dosing. While resident in the CRU, a standard diet (or a Japanese diet, where appropriate) will be provided. When outpatient, a subject's typical diet may be consumed at all other meal times during the study.

Subjects will not be permitted to consume foods containing poppy seeds from 48 hours prior to attending the CRU on Days -1, 8, 29, and 57.

#### **6.3.2. Caffeine, Alcohol, and Tobacco**

Consumption of caffeine- and xanthine-containing products is allowed, provided that the subject's consumption has been consistent for the past 30 days.

Subjects will not be permitted to consume alcohol from 48 hours before each visit until leaving the CRU. Subjects will be advised to abstain from alcohol consumption for the remainder of the trial until their final visit.

Subjects will not be permitted to smoke from CRU admission until discharge from the CRU.

#### **6.3.3. Activity**

Subjects should avoid strenuous exercise and/or activity from 48 hours prior to visits until leaving the CRU.

#### **6.3.4. Male Contraceptive Requirements**

Male subjects, regardless of their fertility status, with non-pregnant female partners of childbearing potential must agree to either remain abstinent (if this is their preferred and usual lifestyle) or use condoms as well as one additional highly effective (less than 1% failure rate) method of contraception (such as combination oral contraceptives, implanted contraceptives, or intrauterine devices) or effective method of contraception (such as diaphragms with spermicide or cervical sponges) for 90 days after study drug dosing.

Men and their partners may choose to use a double-barrier method of contraception. Barrier protection methods without concomitant use of a spermicide are not an effective or acceptable method of contraception. Thus, each barrier method must include use of a spermicide. It should

be noted, however, that the use of male and female condoms as a double barrier method is not considered acceptable due to the high failure rate when these barrier methods are combined.

Male subjects with pregnant partners should use condoms during intercourse for the duration of the study and until the end of estimated relevant potential exposure in women of childbearing potential, predicted to be 90 days following last dose of study drug.

Male subjects should refrain from sperm donation for the duration of the study and until 90 days following last dose of study drug.

Male subjects who are in exclusively same sex relationships (as their preferred and usual lifestyle) are not required to use contraception.

#### **6.4. Screen Failures**

Individuals who do not meet the criteria for participation in this study (screen failure) may not be re-screened. If subjects have minor deviations in screening assessments (e.g., laboratory safety tests, vital signs) these may be repeated at the investigator's discretion to confirm eligibility.

## 7. Treatment

### 7.1. Treatment Administered

This study involves a comparison of LY3478006 administered over a planned single ascending dose range of 10 mg to 1000 mg versus placebo administered by IV infusion, and following a single 100 mg dose versus placebo administered by SC injection. [Table OHAA.3](#) shows the treatment regimens.

In Cohorts 1 through 6, the investigational product will be administered as a slow IV infusion over at least 30 minutes. Sites must have resuscitation equipment, emergency drugs, and appropriately trained staff available during the infusion and for at least 4 hours after subjects have completed their infusion. In Cohort 7, the investigational product will be administered SC in the abdominal wall, approximately 5 cm from the umbilicus and skin biopsy site. If more than 1 SC injection is required, then each injection will be at least 5 cm apart. The site(s) of injection will be recorded.

**Table OHAA.3. Treatments Administered**

Treatment Name	LY3478006	Placebo
Dosage Formulation	Solution for Injection, 200 mg/4-mL	Sterile saline (0.9% sodium chloride)
Unit dose strength(s)/Dosage Level(s)	50 mg/mL Single dose; 10 mg, 30 mg, 100 mg, 300 mg, 600 mg, 1000 mg	N/A Single dose; equivalent volume to each dose level of LY3478006
Route of Administration	Cohorts 1 through 6: IV Cohort 7: SC	
Dosing instructions	Cohorts 1 through 6: slow IV infusion over at least 30 minutes Cohort 7: SC injection via syringe into the abdomen	

Abbreviations: IV = intravenous; N/A = not applicable; SC = subcutaneous.

The investigator or designee is responsible for:

- explaining the correct use of the investigational product(s) to the site personnel
- verifying that instructions are followed properly
- maintaining accurate records of investigational product dispensing and collection (this responsibility can only be performed by unblinded pharmacy staff)
- and returning all unused medication to Lilly or its designee at the end of the study

**Note:** In some cases, sites may destroy the material if, during the investigative site selection, the evaluator has verified and documented that the site has appropriate facilities and written procedures to dispose of clinical materials.

### **7.1.1. Packaging and Labeling**

Clinical trial materials will be labelled as investigational product (IP) as appropriate, and according to the country's regulatory requirements. Clinical trial materials are manufactured in accordance with current good manufacturing practices and will be supplied by Lilly or its representative.

The LY3478006 Injection, 200-mg/vial is supplied as sterile, preservative-free solution in a single-use vial for SC and IV administration. Each milliliter of drug product solution delivers 50 mg of LY3478006.

Placebo for all cohorts is 0.9% sodium chloride (sterile saline).

## **7.2. Method of Treatment Assignment**

Treatment assignment will be determined according to a randomization schedule.

### **7.2.1. Selection and Timing of Doses**

It is planned that all subjects will receive a fixed dose of LY3478006 or placebo, according to the randomization schedule. The planned dose levels are 10-, 30-, 100-, 300-, 600-, and 1000-mg LY3478006, administered IV to subjects in Cohorts 1 through 6, respectively. Subjects in Cohort 7 will receive a planned SC dose of 100-mg LY3478006. However, based on emerging data a higher dose may be administered but will not exceed 300 mg. The actual dose for each cohort will be determined as described in Section [7.4.1](#).

The actual time of all dose administrations will be recorded in the subject's electronic case report form (eCRF). The actual duration time of infusion will be recorded in the eCRF. If the infusion is terminated, this should be recorded in the eCRF.

## **7.3. Blinding**

This is a subject- and investigator-blind study. The study site pharmacist will be unblinded.

To preserve the blinding of the study, a minimum number of Lilly personnel will see the randomization table and treatment assignments before the study is complete.

Randomization tables for allocation of LY3478006 and placebo will be prepared by the Lilly statistician or designee and provided to the study site pharmacists or pharmacy staff involved in dose preparation. Blinding will be maintained throughout the conduct of the study until all data are cleaned to an acceptable level of quality and locked. The details are included in a separate Blinding Plan.

Emergency codes will be available to the investigator. A code, which reveals the treatment group for a specific study subject, may be opened during the study only if the subject's well-being requires knowledge of the subject's treatment assignment.

In case of an emergency, the investigator has the sole responsibility for determining if unblinding of a subject's treatment assignment is warranted for medical management of the event. The subject's safety must always be the first consideration in making such a determination. If the

investigator decides that unblinding is warranted, it is the responsibility of the investigator to promptly document the decision and rationale and notify Lilly as soon as possible.

Upon completion of the study, all codes must be returned to Lilly or its designee.

## 7.4. Dose Modification

### 7.4.1. Dose Decision/Escalation

By nature of being a dose-escalation study, data will be evaluated on an ongoing basis until the maximum planned dose (1000 mg) is reached or a lower dose in the event that the dose escalation stopping criteria are met as described below.

Safety data will be the primary criteria for the dose escalation. In addition, LY3478006 concentrations will be reviewed to guide dose escalation, as described in Section 5.1. ADA results will be reviewed by the sponsor periodically to guide dose escalation, but is not necessary for making dose escalation decisions. No dose decision can occur without prior discussion and agreement between the investigator (or designee) and the Lilly clinical pharmacologist (CP)/ clinical research physician (CRP)/study team. In case of disagreement, the decision of the investigator will be followed, except in a situation where Lilly's proposal is the more conservative action (for example, where the investigator wishes to escalate and the Lilly CP/CRP dose not) in which case, the Lilly proposal will be followed.

Safety data collected through at least Day 15 will be evaluated from at least 6 of 8 subjects prior to each dose escalation. The safety data reviewed will include at least: AEs, clinical laboratory tests, vital signs, ECGs, and neurological/pupillometry examinations.

Safety data, in particular AEs, SAEs, and adverse laboratory abnormalities, will be independently assessed by the investigator, and will be considered related to the investigational product unless there is clear evidence that the event is not related.

After review of these data, an agreement on the appropriate dose escalation will be made by the investigator and sponsor for the next cohort. The magnitude of dose escalations may be reduced following data review, but subsequent escalations cannot be increased by more than approximately 3-fold (a half-log increment).

If any of the following scenarios occur, dosing at the current level and further dose escalation will be discontinued:

- 1) 2 or more subjects experience an SAE or clinically significant event that is related to LY3478006 administration
- 2) 2 or more subjects develop acute AEs of moderate severity that are considered to be related to LY3478006 infusion, during or within 2 hours of completing the infusion, that do not resolve with a reduced infusion rate and/or supportive care (described in Section 7.4.2.2).
- 3) 3 or more subjects at 1 dose level experience moderate treatment-related AEs that impair normal activities

- 4) 2 or more subjects develop AEs within 14 days of dosing that are considered to be related to study treatment and graded as at least moderate, clinically significant and not responsive to supportive care

Dosing may continue in a new dose cohort if the risk-benefit is deemed appropriate by the sponsor and investigator, at a dose reduced by  $\geq 50\%$  of the dose resulting in termination of the dose escalation. Also, it is important to note that when the above criteria are met, any ongoing dosing at a dose level that is below the dose that triggered the stopping rule may continue when considered appropriate by the sponsor.

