#### **7.4.2.2. Management of Infusion Reactions**

There is a risk of infusion reaction with any biological agent; therefore, all subjects should be monitored closely as described in Section 9.4.5.1.

In the event that a significant infusion reaction occurs, the following guidance should be followed:

- The investigational product infusion should be slowed (for example, reduce infusion rate by 50% [for example, an infusion rate of 12 mL/hr becomes 6 mL/hr or slower]) or stopped, depending on the symptoms/signs present:
  - if slowed, the infusion should be completed at the slower rate, as tolerated
  - if determined by the investigator that the infusion should no longer continue, no further attempts to dose the subject should be made; the subject should complete AE and other follow-up procedures per Section 2
- Management of the infusion site reaction should proceed according to the severity of the reaction as described in Section 9.4.5.1.

- If a subject's infusion reaction is sufficiently severe to discontinue the infusion, then subsequent infusions may be administered to subjects with premedication at the discretion of the investigator following agreement with the Lilly CRP or CP (Section 7.4.2.1).
- If a subject's infusion rate is reduced due to an infusion reaction, then subsequent infusions may be administered to subjects at the discretion of the investigator following agreement with the Lilly CRP or CP. If further infusions are administered, the infusion rate must not exceed the slowest rate used to complete the infusion on the occasion the infusion reaction occurred. Premedication may be administered at the discretion of the investigator (Section 7.4.2.1).

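### Stopping criteria 2 and 3 count moderate AEs, not at least moderate ones, so a cohort with one worse event can escape a mandatory stop

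*Protocol*

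**What the plan says.** Protocol Section 7.4.1 (Dose Decision/Escalation) lists four scenarios. If any one occurs, "dosing at the current level and further dose escalation will be discontinued".

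- **Criterion 1** has no severity grade: "2 or more subjects experience an SAE or clinically significant event that is related to LY3478006 administration".
- **Criterion 2** covers infusion events that start during the infusion or within 2 hours of its end and do not resolve with a slower rate or supportive care: "2 or more subjects develop acute AEs of moderate severity that are considered to be related to LY3478006 infusion".
- **Criterion 3**: "3 or more subjects at 1 dose level experience moderate treatment-related AEs that impair normal activities".
- **Criterion 4** needs two or more subjects with related AEs within 14 days of dosing that are "graded as at least moderate, clinically significant and not responsive to supportive care".

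After a stop, a new cohort may be dosed only at a dose reduced by at least 50%. Neither document defines clinically significant event or gives a severity grading scale, and neither says that moderate includes severe. Protocol Section 9.4.4.1 uses severe as a severity term of its own, as one trigger for neurology referral.

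**The concern.** One list uses *moderate* twice and *at least moderate* once, so a reader may fairly take the two terms to differ. If they do, the rule is not monotone in severity. Replacing one moderate event by a severe one can remove a stop that would otherwise be mandatory. The cohort with the worse event then goes to discretionary review, while a cohort with the same number of affected subjects and only moderate events must stop and faces the dose reduction of at least 50%.

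This is a first-in-human study without sentinel dosing (Protocol Section 5.4), and one subject's infusion may start as soon as the previous subject's ends (Section 5.1). The mandatory rules therefore carry weight.

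**Working it through.** The documents give no operating characteristics for the stopping rules, so there is no figure to reproduce. The check has a logical part and an illustrative part.

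**1. Logic.** Assume every event is related and meets all the other conditions of the criterion.

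- *Two moderate + one severe, criterion 3:* the literal count is 2 and 3 are needed, so it is not met.
- *One moderate + one severe infusion event, criterion 2:* the literal count is 1 and 2 are needed, so it is not met.
- *Other routes:* criterion 4 needs related, clinically significant events in two subjects. That already meets criterion 1, so criterion 4 adds no separate route.

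Each event may or may not be an SAE and may or may not be clinically significant. That gives 4 states per subject, of which 3 count under criterion 1.

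- Three subjects: 4³ = 64 combinations. Fewer than two subjects count in 1 + 3×3 = 10 of them.
- Two subjects: 4² = 16 combinations. Fewer than two subjects count in 1 + 2×3 = 7 of them.

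The literal rule fails to stop in exactly those 10 and 7 combinations. With *at least moderate* it stops in all 64 and all 16. These are counts of cases, not probabilities.

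**2. Size, on assumed rates.** Inputs:

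- n = 6 active subjects per cohort (Protocol Section 5.1).
- p = chance that a subject has a qualifying AE of at least moderate severity (assumed).
- q = share of those AEs that are severe (assumed 20%, range 10–30%).
- Every severe event counts as clinically significant and no moderate event does (assumed).

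Two or more severe events then always meet criterion 1. Within one cohort, the only pattern missed is (2 moderate, 1 severe) for criterion 3 and (1 moderate, 1 severe) for criterion 2:

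- P(2,1) = 60 p³ (1−q)² q (1−p)³, where 60 = 6!/(2! 1! 3!)
- P(1,1) = 30 p² (1−q) q (1−p)⁴, where 30 = 6!/(1! 1! 4!)

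Worked cases at q = 0.2:

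- Criterion 3, p = 0.2: 60 × 0.008 × 0.64 × 0.2 × 0.512 = 0.0315
- Criterion 2, p = 0.1: 30 × 0.01 × 0.8 × 0.2 × 0.6561 = 0.0315

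| Pattern | p | Chance per cohort at q = 0.2 |
|---|---|---|
| Criterion 3 (2,1) | 0.1 / 0.2 / 0.3 | 0.6% / 3.2% / 7.1% |
| Criterion 2 (1,1) | 0.05 / 0.1 / 0.2 | 1.0% / 3.2% / 7.9% |

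Over q = 0.1 to 0.3 the extremes are:

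- Criterion 3: 0.4% (p = 0.1, q = 0.1) to 8.2% (p = 0.3, q = 0.3).
- Criterion 2: 0.5% (p = 0.05, q = 0.1) to 10.3% (p = 0.2, q = 0.3).

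**3. Sensitivity.**

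- *Some moderate events clinically significant.* If a share c of them is, the chances are multiplied by (1−c)² for criterion 3 and (1−c) for criterion 2. At c = 0.5 the 3.15% values become 0.8% and 1.6%. At c = 0.9 they become about 0.03% and 0.3%.
- *Placebo subjects' AEs also attributed to drug at the same rate* (n = 8). The middle cases become P(2,1) = 168 × 0.008 × 0.128 × 0.32768 = 5.6% and P(1,1) = 56 × 0.01 × 0.16 × 0.531441 = 4.8%.

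**The case against.** The strongest reply is that no safety team would read *moderate* in a stopping rule as a ceiling, so this is loose drafting with little consequence. The points in support are as follows.

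- **Clinical significance.** A criterion 2 event is acute, related and unresolved despite management, and a criterion 3 event impairs normal activities. Many would be judged clinically significant, and two such subjects meet criterion 1. This stands, and it shrinks the figures as the sensitivity to c shows. But the term is undefined, and a single severe event supplies only one of the two subjects that criterion 1 needs.
- **Severity history.** SAP Section 9.4.1 lists each severity when an AE changes grade. An AE recorded first as moderate and later as severe literally includes a moderate AE. This stands, so the gap concerns AEs recorded only as severe.
- **Joint review.** Safety findings "will be considered related to the investigational product unless there is clear evidence that the event is not related". On dose decisions, "In case of disagreement, the decision of the investigator will be followed", except that a more conservative sponsor position prevails, so either party can block escalation. If an "infusion reaction is sufficiently severe to discontinue the infusion", or if the rate had to be reduced, later infusions given under Section 7.4.2.2 need agreement with the sponsor physician. Protocol Sections 5.4, 9.4.5 and 10.3.4 add further reviews. All this stands, but these provisions are discretionary and do not restore the mandatory stop. Section 7.4.2.2 covers infusion reactions only.
- **Counting across cohorts.** Only criterion 3 is limited to one dose level. If criterion 1 accumulates across cohorts, some (2,1) cases would already stop. This stands as a limit on the criterion 3 figure. Criterion 2 is not limited to one dose level either, so its mixed pattern could also arise across cohorts.
- **Assumed rates.** The percentages are illustrative. They give the chance that a pattern occurs, not the chance that dosing wrongly continues.

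**Conclusion.** The concern holds. As written, criteria 2 and 3 drop a mandatory stop in the two mixed patterns unless at least two subjects have a related SAE or clinically significant event. That follows from the text and needs no assumed rate.

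The practical gap is narrow. If severe events always count as clinically significant, only the two mixed patterns remain, and only where the moderate events are judged not significant and the severe AE was never recorded as moderate. If severe events do not always count, patterns such as three severe events are missed too.

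Under the assumptions above, each pattern has a middle-case chance of about 3.2% per cohort, falling to 0.8% (criterion 3) and 1.6% (criterion 2) if half of the moderate events are judged significant. The intent was very likely *at least moderate*. A severity reversal in a first-in-human stopping rule should be corrected even at these probabilities.

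**What to change.** In Protocol Section 7.4.1:

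- Criterion 2: change *of moderate severity* to *of at least moderate severity*.
- Criterion 3: change *moderate* to *at least moderate*.

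This matches criterion 4. It adds stops only in cases at least as serious as those that already force one. The cost is two words in each of two criteria, with no new data, visits or subjects.
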